1.1 Study Objectives

Primary objective

[figure not shown]
To assess the efficacy of the diabetes-specific Cognitive Behavioral Therapy (CBT) versus control in helping patients with Type 2 diabetes (T2D) and depressive symptoms to achieve glycemic control. Primary endpoint: change of glycated hemoglobin A1c (Hb A1c) level three months after the intervention.

Secondary objective

Estimate the efficacy of CBT in improving depressive symptoms among T2D patients. Secondary endpoint: change of depression score on Beck's Depression Index (BDI).

1.2 Study Design

Prospective, randomized, parallel group, two-arm controlled trial comparing CBT vs control groups after two months of CBT intervention.

2 Analysis Populations

The study population is defined by the following key inclusion and exclusion criteria:

Key inclusion criteria

- Uncontrolled type 2 diabetes mellitus (HbA1c $\geq 6.5\%$)
- Mild mood disturbance to Moderate depression (BDI)
- 35 to 80 years of age
- Able to give informed consent and understand given information.

Key exclusion criteria

- Type I diabetes
- Psychiatric disorders other than depression or personality disorders including schizophrenia, bipolar disorder, and substance or alcohol abuse.
- Depressed patients on treatment for depression
- Suicidal patients and those diagnosed with major depressive disorder will be referred to a psychiatrist.

3 Study Centre

Al-Agouza Family Medicine Center (AFMC) is a primary healthcare center in Giza, Egypt. The AFMC patient registry (database) currently has more than 1370 family medical records. It has been maintained since 2011. It has been estimated at 11% of patients in the database are diabetics and between 48-96 new diabetic patients are seen each year.

4 Data Collection Tools

A structured questionnaire will be used to collect data from the study participants. The questionnaire includes the following:

4.1 Demographic (age, residence, gender, marital, status, education level, occupation).

4.2 Diabetes History and Health Behavior Questionnaire

4.3 Measure Treatment Adherence (MTA)

To assess patients' adherence to diabetes medications, the Measure Treatment Adherence (MTA) modified scale will be used (Morisky et al. 1986; Delgado & Lima 2011). Several studies had validated the scale (Lopes et al. 2008; Shams & Barakat 2010). MTA Scale consisted of six questions and allowed answers from "always" to "never," with scores ranging from 1 to 4 points. The highest values indicated the highest level of adherence to treatment. Adherence score will be considered as follows:

- More than 75%- good adherence
- Between 50%-75%- poor/partial adherence
- Less than 50%- non-adherence

4.4 Beck's Depression Inventory (BDI)

Moreover, depression will be assessed using BDI (Lustman, Clouse, Griffith, Carney, & Freedland, 1997) as recommended by the research psychiatrist. BDI is a 21-question multiple-choice self-report inventory, used for measuring the severity of depression. A value of 0 to 3 will be assigned for each answer and then the total score will be compared to a key to determine the depression's severity. The standard cut-off scores will be

as follows:

- 1-10 These ups and downs are considered normal
- 11-16 Mild mood disturbance
- 17-20 Borderline clinical depression
- 21-30 Moderate depression
- 31-40 Severe depression
- over 40 Extreme depression

4.5 Structured Clinical Interview for Diagnostic and Statistical Manual of Mental Disorders, 4th Edition (SCID-IV)

The SCID-IV (Glasofer et al. 2015) will be used to diagnose patients with mood disorders and exclude other psychiatric morbidities.

4.6 Anthropometric and Biochemical Measures

The anthropometric measurements will be performed. The weight in kg and height in cm will be measured using the UGM-200 health scale with barefoot patients, wearing light clothes, and looking at the horizon. The waist circumference in centimeters will be measured on bare skin, mid-distance between the bottom of the rib cage and the top of the iliac crest using an inelastic tape. The BMI will be calculated by dividing the weight by the height squared (BMI= weight in kg/height in cm²) (Cashin & Oot 2018).

To assess diabetes control, Fasting Plasma Glucose (FPG), 2-hour Plasma Glucose (2-h PG), and HbA1c will be performed at the AFMC clinical laboratory. Subsequently, participants will be randomized to control and treatment groups if they met our inclusion criteria.

5 Intervention

5.1 Diabetes Education Message

All eligible patients will be offered a structured diabetes education by a trained educator as an update to ensure adequate diabetes knowledge in all trial participants. A one-session message for 30-40 minutes and covered the following:

- Pathophysiology of DM
- Early detection of diabetes symptoms
- Risk and predisposing factors
- Recognition of diabetes complications
- Self-care including diabetes-relevant behavior (e.g., nutrition, physical activity, foot care)
- Monitoring and treatment of diabetes

5.2 Cognitive Behavioral Therapy Program

The treatment group will receive four CBT sessions twice a month for two months. The control group will be scheduled the same number of visits as a follow up for DM.

Patients in the CBT intervention group (Safren & Gonzalez 2007) received four educational sessions for 30-45 minutes once every two weeks during patients' regular follow up visits. The visits will be scheduled depending on the patient's availability. The sessions will be delivered by a trained physician. They will be on one to one basis and will be held at the AFMC outpatient clinic. The sessions included:

- Session 1: Dealing with thoughts of sadness and depression
- Session 2: Dealing with thoughts of anxiety and stress
- Session 3: Dealing with anger
- Session 4: Enhancement of coping and problem-solving skills

During the sessions, each participant worked with the healthcare provider to:

STEP 1: Identify thoughts and determine their effect on actions and feelings. Some examples include:

- a. Thoughts
 - o "What have I done to deserve this?"
 - o "This illness is some kind of punishment for bad things I have done"
 - o "I'll never find anyone who will love me."
- b. Feelings

- o "I'm a failure because I have diabetes"
- o "I am unlovable because of this illness and how I am managing it"

c. Actions

- o "There is nothing I can do to stop diabetes complications"
- o "There is no way I can manage everything I need to for diabetes"
- o Not meeting anyone, spending the weekends alone at home

STEP 2: Challenge Thoughts, analyze each thought to work out if it has been realistic or unhelpful. This can be achieved by asking questions such as:

- o What is the evidence for and against this thought?
- o Is thinking this way helping me?
- o Is there really nothing you can do?

STEP 3: Think of an alternative, balanced thought the physician will help patients change unhelpful thoughts and behaviors by teaching them some skills during they could apply daily. "I may not be able to control whether I develop complications, but I can feel in control of trying my best to keep healthy"

- o "The research shows that those who test their blood are healthier and less likely to develop long term complications"

Patients will be encouraged to practice these changes in their daily life and discuss how they got on during the next session. This should help patients manage daily life problems and stop them from having a negative impact on their life. Patients will be encouraged to set a diabetes-specific goal in order to improve their glycemic control such as weight loss or HbA1c target values and try to achieve it at the end of the sessions.

Adherence to CBT has been determined by the number of CBT-sessions attended by participants and will be defined as follows:

- Adherent participation- 3-4 sessions of CBT
- Partially non-adherent participation- 1–2 sessions of CBT
- Non-adherent
- No participation in any session of CBT

6 Post-intervention

In the last visit three months later, all participants will be reassessed for depression using BDI and diabetes compliance using the MTA modified scale. All required labs (FPS, 2-h PG, and HbA1c) will be reperformed.

7 Treatment of Missing Values and Outliers

Appropriate methods will be employed on an individual basis for the missing values and variables normalization. The primary analyses for HbA1c and the BDI scores will be repeated after employing the last observation carried forward method (LOCF). The multiple imputation method will be employed when more than 10% but less than 40% of the values will be missing (Pedersen et al., 2017). If outliers will be apparent to bias the analysis, they will be set to missing.

8 Analysis Variables

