9.2 Analysis of Outcomes

9.2.1 primary analysis

The primary variable is the Hb A1c plasma level.

The primary endpoint is the difference between Hb A1c level at baseline and three months later.

The primary outcome is the change of Hb A1c, compared between the different treatment groups using an Analysis of Covariance (ANCOVA), the General Linear Modeling approach to compare the study groups. The HbA1c and BDI at baseline will serve as control variables. HbA1c and BDI values at baseline are the values obtained at

the first visit before the start of the intervention. If the HbA1c value at baseline is missing, the first HbA1c value obtained during the first subsequent visits will be used.

The following hypothesis will be tested:

$H_0: \mu_{CBT} = \mu_{control}$ versus $H_1: \mu_{CBT} \neq \mu_{control}$

Where μ_{CBT} and $\mu_{control}$ are the expected mean values of the differences in HbA1c values belonging to the CBT and the control groups. The hypothesis will be tested on a 2-sided p-value with alpha ≤ 0.05 level of significance. The results will be displayed by means of the p-value, standard deviation of unadjusted values, and 95%-confidence interval. For that, the assumption of homogeneity of regression slope will be examined by testing the interaction effect of the independent variable and the covariate.

The secondary variable is the BDI score.

The secondary endpoint is the difference between BDI at baseline and three months later.

The secondary outcome is the change of BDI compared between the different study groups using an Analysis of Covariance (ANCOVA), the General Linear Modeling approach to compare the study groups. The HbA1c and BDI at baseline will serve as control variables. HbA1c and BDI values at baseline are the values obtained at the first visit before the start of the intervention. For that, the assumption of homogeneity of regression slope will be examined by testing the interaction effect of the independent variable and the covariate.

The following hypothesis will be tested:

$H_0: \mu_{CBT} = \mu_{control}$ versus $H_1: \mu_{CBT} \neq \mu_{control}$

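### The planned LOCF repeat enters zero change for patients who miss the only scheduled follow-up, so this robustness check can be biased in either direction

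*Combined protocol and SAP*

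**What the plan says.** Section 7 plans a repeat of both outcome analyses: "The primary analyses for HbA1c and the BDI scores will be repeated after employing the last observation carried forward method (LOCF". It names a second method for one range of missingness: "The multiple imputation method will be employed when more than 10% but less than 40% of the values will be missing". It does not say whether that imputation is main or supportive, or how its result is to be read beside the LOCF repeat.

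Each outcome is scheduled twice. Section 4.6 puts the first assay before randomisation ("HbA1c will be performed at the AFMC clinical laboratory"). Section 6 puts the second measurement at the final visit: "In the last visit three months later, all participants will be reassessed for depression using BDI", and "All required labs (FPS, 2-h PG, and HbA1c) will be reperformed". Section 9.2.1 defines the endpoint to match: "The primary endpoint is the difference between Hb A1c level at baseline and three months later". The BDI endpoint has the same form.

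Three other wordings bear on timing. Section 1.1 has "change of glycated hemoglobin A1c (Hb A1c) level three months after the intervention". Section 9 speaks of HbA1c when the sessions finish. Section 9.2.1 gives a fallback: "If the HbA1c value at baseline is missing, the first HbA1c value obtained during the first subsequent visits will be used". None of these schedules a further assay, and the fallback serves only a missing baseline. BDI has no such fallback.

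**The concern.** With one follow-up measurement there is normally nothing to carry forward except baseline. LOCF then becomes the single assumption that every dropout stayed exactly where they started, entered as if it had been measured.

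A robustness check should show how far the conclusion depends on what is not seen. This one tests one value and cannot show how the result moves if that value is wrong. With unequal loss it may point away from a correct main result, or seem to support a wrong one. At 10% missing or less, and at 40% or more, it is the only imputation method that section 7 names.

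**Working it through.** **Inputs.** From the documents: two scheduled measurements (sections 4.6, 6 and 9.2.1); ANCOVA of change on group, baseline HbA1c and baseline BDI, two-sided 0.05 (section 9.2.1); a calculated sample size of 80 (section 10.1); about 100 eligible and willing (section 12.3). The figure of 80 cannot be reproduced, because no effect, SD, power or dropout rate accompanies it. Assumed: 40 per arm (50 per arm as a variant), residual SD of HbA1c change 1.2, true difference -0.60 or 0, dropout random within arm, and dropouts who change like completers unless stated.

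**Step 1, bias.** In one arm let d be the dropout share, c the completers' mean change and m the dropouts' true mean change. The true arm mean is (1-d)c + dm. LOCF gives (1-d)c + d x 0. The error per arm is -dm, so the error in the difference is

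bias = -(d_CBT x m_CBT - d_ctrl x m_ctrl).

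It is zero if dropouts do not change or if the two products are equal. Examples:
- 20%/20% loss (CBT/control), changes -0.6/0: -(0.20 x -0.6 - 0) = +0.12, so -0.60 becomes -0.48.
- 30%/10% loss, changes -1.2/-0.6: -(-0.36 + 0.06) = +0.30, giving -0.30.
- 10%/30% loss, changes -1.2/-0.6: -(-0.12 + 0.18) = -0.06, giving -0.66.
- 10%/30% loss, changes -0.9/-0.3: both products are -0.09, so LOCF stays at -0.60.
- 30%/10% loss, both arms -1.0 (no true effect): -(-0.30 + 0.10) = +0.20.

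**Step 2, effect on the test.** Simulation of the planned ANCOVA, 20,000 trials per scenario, 40 per arm:

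| Loss CBT/control | True change CBT/control | LOCF estimate | Rejection, observed data | Rejection, LOCF |
|---|---|---|---|---|
| 5%/5% | difference -0.60 | -0.57 | 57% | 57% |
| 20%/20% | -0.6/0 | -0.48 | 49% | 49% |
| 20%/20% | -1.2/-0.6 | -0.48 | 49% | 45% |
| 13%/3% | -0.6/0 to -1.2/-0.6 | -0.52 to -0.46 | 55% | 50% to 40% |
| 30%/10% | -0.6/0 | -0.42 | 48% | 38% |
| 30%/10% | -0.9/-0.3 | -0.36 | 48% | 29% |
| 30%/10% | -1.2/-0.6 | -0.30 | 48% | 20% |
| 10%/30% | -1.2/-0.6 | -0.66 | 48% | 73% |

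In the three 30%/10% rows, LOCF coverage of the true -0.60 is 88%, 84% and 79%. In the last row a trial with no dropout would reject 58% of the time. With no true effect, 30%/10% loss and both arms improving by 0.6 or 1.0, the LOCF type I error is 7.6% or 12.4%. With 25%/15% loss it is 5.7% or 6.9%, and with 20%/20% loss 5.0% to 5.3%. With 50 per arm the worst cases are slightly worse: 75% coverage and 13.8% type I error.

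**Step 3, standard error.** The LOCF variance in an arm with mean change m is (1-d)SD^2 + d(1-d)m^2. This is below SD^2 only when (1-d)m^2 < SD^2.
- HbA1c, 20%/20% loss, changes -0.6/0: CBT 0.8 x 1.44 + 0.16 x 0.36 = 1.2096; control 1.152. The unadjusted standard error is sqrt(2.3616/40) = 0.243, against sqrt(2.88/40) = 0.268 with no dropout and sqrt(2.88/32) = 0.300 in completers. The ANCOVA simulation gives about 0.25, 0.27 and 0.30.
- BDI, assumed SD 6, changes -12/-8: at 20% loss (1-d)m^2 is 115.2 and 51.2, both above 36, so the condition fails. The simulated LOCF standard error is 1.46, 1.52 and 1.55 at 10%, 20% and 30% loss, against 1.36 with no dropout. Here it rises with loss.

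For HbA1c at 20% loss per arm, the mean LOCF standard error is 0.245 to 0.258 and the actual spread of LOCF estimates is 0.243 to 0.245.

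**Step 4, BDI.** An assumed SD of 8 and difference of -4 has the same ratio as -0.60 to 1.2. At 20%/20% loss LOCF gives -3.2. At 30%/10% loss, with control changes of 0, -2 and -4, it gives -2.8, -2.4 and -2.0. The HbA1c rejection rates carry over only for those scaled control changes.

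**The case against.** The strongest defence is that no-change can be the right assumption. With 30%/10% loss, completers changing by -0.9/-0.3 and dropouts truly unchanged, the true difference is 0.7 x -0.9 - 0.9 x -0.3 = -0.36. LOCF recovers that, while observed-data ANCOVA and unshifted imputation give -0.60. This stands, and it is a reason to keep no-change in view as one scenario.

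It is also fair that LOCF is only a repeat, that multiple imputation is planned for the middle range of missingness, and that the serious figures need unequal loss together with improvement in both arms. Diabetes education for all eligible patients (section 5.1) makes some common improvement plausible, but the documents give no figure for it or for dropout.

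A reader might infer that LOCF always looks more precise as dropout rises. Step 3 shows otherwise: this is likely for modest HbA1c changes but may fail for large BDI changes. A reader might also infer that its standard error is too small. For the LOCF estimate itself it is about right; the fault is that the interval sits around a biased value. Finally, section 9.2.1 allows that an earlier HbA1c may exist for some patients, so for HbA1c the zero is conditional.

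**Conclusion.** The point holds as an improvement to the robustness check. On the documented schedule the LOCF repeat tests one assumption, zero change in dropouts, and is biased by the formula in step 1 whenever that assumption fails and the arms' products differ. With low or equal loss the effect on testing is small. With 30%/10% loss and improvement in both arms it is material: under the assumed inputs, -0.60 shrinks to as little as -0.30, or the type I error reaches about 12%. Loss in the opposite pattern can exaggerate the effect. The direction and size in this trial cannot be known from the documents.

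A reader might go further and conclude that the main ANCOVA is compromised, or that an observed-data ANCOVA must now be declared the main result. The documents support neither. LOCF is not the main analysis, and section 7 leaves the role of multiple imputation open, so this point gives no ground for choosing between them.

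**What to change.** In section 7, stop relying on LOCF as the robustness check and add text such as:

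> At whatever level of missingness occurs, the section 9.2.1 ANCOVA for HbA1c and for BDI will be repeated after multiple imputation, with a shift (delta) added to the imputed outcomes of dropouts. The shift will be varied separately by arm until the conclusion changes. No change from baseline will be one labelled point on this grid. The LOCF result, if reported, will be labelled as the no-change scenario.

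The imputation can use variables already collected: arm, baseline HbA1c and BDI, age, sex, baseline MTA score, diabetes treatment type, and sessions or visits attended. One model with arm as a term costs less precision than separate models by arm (standard error 0.32 against 0.33 at 20% loss per arm). Keep the planned multiple imputation, and do not change which analysis is the main one. Section 12.3 says that the trial has reached analysis and section 9 describes a blinded statistician, so date the addition and record whether it came before unblinding.

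The cost is modest extra analysis, a documented late addition and a wider sensitivity interval: standard error about 0.32 against 0.25 for LOCF at 20% loss per arm, and 0.29 against 0.26 at 8% missing (13%/3%), both with the assumed SD of 1.2. At the no-change point the pooled standard error is conservative (0.324 against an actual spread of 0.262). Under random dropout the imputation removes no bias that observed-data ANCOVA would have; its purpose is to carry the shifts.

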8.2.6 Adherence to treatment

Type of diabetes medication (table/insulin); assessment for adherence based on MTA scale (%); and reasons for non-adherence (ineffective/side effects/forgetful/expensive/better without treatment) will be recorded. Adherence data will be presented by appropriate descriptive statistics (mean, standard deviation, median, and interquartile range (IQA). Exploratory p-values of the t-test and chi-square between treatment groups will be calculated.

The number of study CBT sessions and visited attended by the study groups will be recorded and presented as number and percentage.

9 Statistical Analysis

The analysis will be conducted according to the Consolidated Standards of Reporting Trials guideline (CONSORT). An academic statistician blinded to study groups conducted the study statistical analysis. Quantitative data will be examined for normality distribution using the Shapiro-Wilk's test ($p>0.05$) (Shapiro & Wilk 1965; Razali & Bee Wah 2011) test. Results of $p<0.05$ will be considered significant indicating non-normal distribution. A parametric Levene's test will be used to verify the equality of variances in the samples (homogeneity of variance) ($p>0.05$) (Nordstokke, & Zumbo 2010; Nordstokke et al. 2011).

Simple frequency distribution tables to provide a description for both groups will be generated. Quantitative variables will be summarized using. mean and standard deviation (SD) for normally distributed quantitative variables and median and interquartile ranges (IQR) for not normally distributed quantitative variables. While the number and percentage will be used to summarize qualitative variables.

Exploratory p-values of the student two-tailed independent t-test and Chi-Square test between study groups will be used for baseline quantitative and qualitative variables, respectively. P-values will be reported to three decimal places with p-values less than 0.001 reported as $p < 0.001$. We used 2-sided p-values with alpha ≤ 0.05 level of significance.

Two sets of analyses will be conducted corresponding to the study outcomes' endpoints: 1) the CBT group demonstrated improvement of HbA1c level at the end of the sessions and 2) the CBT group demonstrated improvement of depression score on BDI versus the control group.

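### Section 7 sets outliers to missing with no criterion and no protection for genuine values, and the LOCF repeat does not reveal what was removed

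*Combined protocol and SAP*

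**What the plan says.** Section 7 has one sentence on outliers: "If outliers will be apparent to bias the analysis, they will be set to missing". On missing data it says "Appropriate methods will be employed on an individual basis for the missing values and variables normalization", and then "The primary analyses for HbA1c and the BDI scores will be repeated after employing the last observation carried forward method (LOCF"). Multiple imputation is planned when more than 10% but less than 40% of values are missing.

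Three other places bear on the rule:

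- Section 6 schedules one reassessment of HbA1c and BDI, at the last visit. For the laboratory tests: "All required labs (FPS, 2-h PG, and HbA1c) will be reperformed".
- Section 9.2.1 says of the primary variable: "If the HbA1c value at baseline is missing, the first HbA1c value obtained during the first subsequent visits will be used".
- Section 9 says: "An academic statistician blinded to study groups conducted the study statistical analysis".

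No section defines an outlier, limits removal to errors, or plans an analysis with all observed values kept.

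**The concern.** The rule is an instruction to delete data, and its trigger is whether a value seems to distort the result. That can only be judged with the analysis in view, and Section 12.3 says the trial is already in the data analysis phase. Blinding the statistician to groups limits deliberate selection by arm. It does not fix the cut-off, and it does not hide the size of a difference or its p-value.

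A patient whose depression or glycaemic control clearly worsened is an outcome the trial exists to count. Under this rule the same data can give different HbA1c and BDI results, depending on a choice made at analysis. Dropping patients who got worse favours CBT if they are in the CBT arm and works against CBT if they are in control. The only planned repeat of the primary analyses, LOCF, would not show that this had happened.

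**Working it through.** The plan gives no figure for this point to reproduce. The only design number is the total of 80 (Section 10.1), stated without effect size, SD or power. I take 40 per arm (1:1 assumed), and 50 per arm for the roughly 100 who accepted (Section 12.3). Means, SDs and cut-offs below are assumptions.

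**1. Can genuine values be extreme?** Section 4.4 describes 21 items, and "A value of 0 to 3 will be assigned for each answer", so the maximum is 21 × 3 = 63. Entry covers mild mood disturbance to moderate depression, 11 to 30 on the listed bands, which leaves room for large rises. HbA1c entry is 6.5% or more with no upper limit, so baseline is probably right-skewed. Section 10.2 names worsening depression as a risk, while calling it rare.

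**2. Where does a removed value go?**

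- Last-visit value, main ANCOVA: the patient drops out by default.
- Last-visit value, LOCF repeat: baseline is carried forward, so the change is 0.
- Above 10% missing in total (more than 8 of 80): multiple imputation fills the gap from the remaining data.
- Baseline HbA1c: read literally, Section 9.2.1 substitutes the last-visit value, the only later one scheduled, so the change is 0 in the main analysis.

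In none of these does the observed value return.

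**3. BDI arithmetic.** Two patients rise by 15; all others change by -4 (CBT) or -1 (control). Unadjusted CBT minus control, 40 per arm:

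| Placement | All data | Dropped | LOCF |
|---|---|---|---|
| Both in CBT | (38×(-4)+30)/40 + 1 = -2.05 | -4 + 1 = -3.00 | (38×(-4))/40 + 1 = -2.80 |
| Both in control | -4 - (38×(-1)+30)/40 = -3.80 | -3.00 | -4 - (38×(-1))/40 = -3.05 |
| One in each | -2.93 | -3.00 | -2.93 |

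Given two such patients placed at random, each same-arm case has probability 40×39/(80×79) = 0.247, and the split 0.506. At 50 per arm the first two rows are -2.24 / -3.00 / -2.84 and -3.64 / -3.00 / -3.04.

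**4. LOCF against deletion.** A separate simulation assumed a CBT effect of -0.5 SD, with genuine +3 SD worsening in 10% of control and 2.5% of CBT patients. The all-data estimate was -0.73 SD. Deletion at pooled 3 / 2.5 / 2 SD gave -0.67 / -0.61 / -0.51; LOCF on the same data gave -0.67 / -0.59 / -0.48. LOCF follows the deleted-data result and does not return towards -0.73.

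**5. Chance of a significant CBT benefit on BDI.** Planned ANCOVA, two-sided 0.05; baseline N(19,6) truncated to 11-30; mean changes -4 and -1; slope on baseline -0.3; 10,000 trials.

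| Scenario | No removal | After removal |
|---|---|---|
| Two +15 in CBT, SD 5 (rule on change) | 33% | 74% (1.5 IQR within arm), 70% (1.5 IQR pooled), 49% (3 SD pooled), 38% (3 IQR within arm), 34% (3 IQR pooled) |
| Two +15 in CBT, SD 7 | 20% | 31-33% (1.5 IQR within arm), otherwise 19-25% |
| Two +15 in control, SD 5 (rule on change) | 89% | 75-81% (1.5 IQR), 83% (3 SD pooled), 88-89% (3 IQR) |
| Two +10 in CBT, SD 5 | 49% | 59-62% (1.5 IQR within arm), otherwise 48-54% |

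**6. False positives, no patient placed by hand.** Equal arms, normal or t(5) errors, rules on change, 20,000 trials, 40 per arm:

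| Rule | Fixed rule | Kept or removed after seeing the result (smaller p; upper bound) |
|---|---|---|
| No removal | 4.8-5.3% | n/a |
| 1.5 IQR within arm | 7.2-8.1% | 7.8-9.3% |
| 1.5 IQR pooled | 4.7-5.3% | 5.9-6.9% |
| 3 SD pooled or 3 IQR within arm | 4.7-5.3% | 5.1-6.0% |

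At 50 per arm, 1.5 IQR within arm gives 6.9-7.2%. Repeat runs at 40 per arm gave 7.0-7.7% for that fence, and 4.8-5.4% for pooled cut-offs of 2 to 3 SD.

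**7. HbA1c, no patient placed by hand.** Baseline 6.5 + gamma (mean 8.5, SD 1.5), mean changes -0.8 and -0.3, slope -0.3, residual SD 1.0. A 1.5 IQR fence flags about 3 of 80 genuine baselines (at least one in 93-95% of trials); 3 SD flags about 1; 3 IQR about 0.5. With the Section 9.2.1 substitution and flagged last-visit values dropped, a difference of -0.50 becomes -0.47 to -0.50, and power goes from 59% to 54-59%. If CBT works better at higher baseline (-0.2 per point), -0.49 becomes -0.42 to -0.48, and power goes from 56% to 44-54%.

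**The case against.** The strongest reply is that the damaging figures come from an unlikely scenario and one strict rule.

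- Under N(-4, 5), a rise of 15 or more has probability 0.00007 per patient, and at least two among 40 about 0.000004. At SD 7 the figures are 0.003 and about 0.8%. With no patient placed by hand, power on BDI at SD 5 is 78% with all data and 75-78% under the rules tested; at SD 7 it is 46% and 44-49%. This stands: for ordinary data most rules change little, and the 33% to 74% contrast is a scenario, not a forecast.
- Only the within-arm 1.5 IQR fence exceeds 5% as a fixed rule, and an automatic fence is not the most natural reading of Section 7. This also stands, but nothing in the plan excludes it.
- The HbA1c effect is small and towards the null, so it does not flatter CBT. The larger loss needs an interaction that the documents do not mention. Correct.
- The baseline substitution may be meant for early visits, and the plan does not say that it applies to a measured value later deleted. Fair. No interim HbA1c is scheduled, however, so the literal reading leads to the last visit.
- Section 7 does not say whether LOCF comes before or after outlier removal, and LOCF is not offered as an outlier check. On the plain reading, a value set to missing is one that LOCF fills. If raw values were kept in that repeat, outlier and missing-data effects would be mixed.

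None of this supplies a criterion or protects a verified value.

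**Conclusion.** The concern holds. Section 7 directs the removal of values on a judgement made from the analysis, with no definition and no exception for genuine results, and no planned analysis keeps all observed values. It should be corrected, but it does not by itself invalidate the trial.

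The textual finding needs no assumptions. The sizes do: false positives of about 7-8% on both endpoints under a within-arm 1.5 IQR fence, and about 5% under the pooled and wider rules tested. BDI shifts of up to 0.95 points arise only if two patients with rises of 15 fall in the CBT arm, with a smaller shift the other way if both are in control. The HbA1c change is small unless the CBT effect varies with baseline. Confidence in the magnitudes is medium. That the answer depends so much on the rule is the reason to state it.

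**What to change.** 1. Replace the outlier sentence in Section 7 with: *No verified BDI score (0-63) or physically possible HbA1c value is set to missing as an outlier; only confirmed entry or laboratory errors are corrected or removed, before the group comparison is run.*
2. Keep any analysis without extreme values as a labelled sensitivity analysis with its rule stated, for example 3 SD of change with the arms pooled. Do not use a 1.5 IQR fence within arm.
3. List every value removed, by arm and direction.
4. State in Section 9.2.1 that the baseline HbA1c substitution is not used for a value removed as an outlier.
5. If values have already been removed, report the results with and without them.

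A stated criterion applied blind to group would also close the gap in definition, but it would still discard genuine outcomes from the main analysis.

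No new data are needed: one sentence in Section 7 and one in Section 9.2.1. Because the trial is in the data analysis phase, the change must be dated and cannot be presented as pre-specified, so item 5 matters most if removal has begun. The statistical cost is a larger SD when valid extremes are kept. With one BDI rise of 15 in each arm (SD 5), the chance of a significant CBT benefit is 66% with all data and 78% after 1.5 IQR removal within arm.
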